11	7.	Immune response including prevalence of hypersensitivity-related outcomes (e.g., asthma, atopic
12		dermatitis; higher levels of immunoglobulins (IgG, IgA and IgM) and lower antibody responses to
13		rubella, mumps, and diphtheria vaccines).
14	Neuroo	developmental outcomes (lower intelligence quotient (full scale IQ), attention-deficit and
15	hypera	ctivity disorder (ADHD).
16	For adu	ults (aged \geq 18 years), the Multi-site Study will evaluate the following main hypotheses.
17	Higher	serum levels of PFOA, PFOS, PFHxS, or other PFAS are associated with:
18	1.	Lipids (higher total cholesterol, low-density lipoprotein and triglycerides) and a higher prevalence
19		of hypercholesterolemia).
20	2.	Higher prevalence of coronary artery disease and hypertension (including hypertensive disorders
21		of pregnancy).
22	3.	Renal function (higher level of uric acid and a higher prevalence of hyperuricemia, lower
23		estimated glomerular filtration rate (eGFR)) and higher prevalence of kidney disease.
24	4.	Glycemic parameters (glucose, insulin, glycosylated hemoglobin (HbA1c), auto-antibodies (GAD-
25		65 and IA-2), C-peptide, pro-insulin) and diabetes (type 1 and 2).
26	5.	Differences in thyroid hormones (thyroid stimulating hormone (TSH), TT4, FT4, and TT3), and
27		higher prevalence of hypothyroidism/ hyperthyroidism.

1	6.	Liver function/damage biomarkers (alanine transaminase (ALT), γ -glutamyltransferase (GGT),
2		direct bilirubin, cytokeratin-18 (CK-18)) and liver disease.
3	7.	Higher prevalence of osteoarthritis and osteoporosis.
4		
5	8.	Higher prevalence of endometriosis.
6	9.	Measures of immune response and inflammation (serum levels of IgA, IgE, IgG, IgM, C - reactive
7		protein (CRP), antinuclear antibodies (ANA), inflammatory cytokines and adipokines (interleukin
8		1- β (IL-1 β), interleukin 6 (IL-6), interleukin 8 (IL-8), monocyte chemotactic protein-1 (MCP-1),
9		tumor necrosis factor α (TNF α), leptin, adiponectin, resistin, plasminogen activator inhibitor-1
10		(PAI-1).
11	10	Higher prevalence of autoimmune diseases such as ulcerative colitis, rheumatoid arthritis, lupus,
12		and multiple sclerosis.
13		
14	2.6 Int	ended Use of Study Findings
14	2.0 m	
15	Given t	hat epidemiological research on the health effects of drinking water exposures to PFAS other than
16	PFOA i	s at an early stage, the Multi-site Study should make an important contribution to the scientific

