and average PFAS serum levels. The primary analyses will evaluate each PFAS chemical separately; sum

of PFAS measures may also be considered. Statistical analyses using prevalent cases in a cohort design 1 2 which takes into consideration the times of diagnosis will also be conducted. ATSDR will explore the use 3 of methods for evaluating multi-pollutant mixtures, such as the hierarchical Bayesian model, to analyze 4 the effects of exposures to the PFAS mixtures. ATSDR will use quantitative methods to assess the impact 5 of possible selection bias and possible confounding due to unmeasured risk factors (Lash 2009). There 6 are several caveats and recommendations in conducting analyses of mixtures to determine the optimal 7 method that avoids amplifying bias due to confounding (Weisskopf et al 2018). For the bias analyses, ATSDR will identify "negative control" diseases with no known association with PFAS exposures (Lipsitch 8 9 2010). ATSDR conducted a literature search to identify these negative control diseases and included them 10 in the questionnaire.

ATSDR will interpret the findings from this study based on the magnitude of the effect estimates (e.g., the linear regression coefficient for continuous outcomes or the odds ratio for categorical outcomes) of the exposure-response relationship, consistency with findings from other studies, and the possible sources of bias (Rothman 2014). The analyses will construct confidence intervals to indicate the level of precision (or uncertainty) in the effect estimates.

The studies will use statistical significance testing to interpret findings but will not use it as a sole factor in determining scientific and public health significance (Rothman et al. 2008, 2010; Stang et al. 2010). A finding that fails to achieve statistical significance can still provide evidence for a causal association, and a finding that achieves statistical significance can lack any such significance (Porta 2014).

20 4. RESULTS REPORTING

21 4.1 Notification of Individual Results

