Assuming a 95% CI and 95% power, the sample size = 68/group.

a. TSH

In Ji 2012, the sample size was 633, \geq 12 years of age and the median TSH level was 1.37 µIU/mL with an IQR of 0.90, 2.01. The standard deviation was estimated as the IQR range divided by 1.35: (2.01 - .90)/1.35 = 0.82. This standard deviation was assumed for each group. For TSH, the linear regression coefficients for PFOS and PFHxS were 0.062 and 0.013, respectively. Using a PFOS level of 15 ng/mL and a PFHxS level of 9 ng/mL, the mean difference for PFOS and PFHxS are 0.93 and 0.12, respectively.

Assuming a 95% CI and 80% power, the sample size = 13/group for PFOS

Assuming a 95% CI and 80% power, the sample size = 733/group for PFHxS

b. TT₄ (total thyroxine)

In Ji 2012, the sample size was 633, \geq 12 years of age and the median TT₄ level was 7.4 µg/dL and the IQR was 6.7, 8.1. The standard deviation was estimated: (8.1 – 6.7)/1.35 = 1.04. This standard deviation was assumed for each group. For TT₄, the linear regression coefficients for PFOS and PFHxS were -0.021 and - 0.007, respectively. Using a PFOS level of 15 ng/mL and a PFHxS level of 9 ng/mL, the mean difference for PFOS and PFHxS are -0.32 and -0.06, respectively.

Assuming a 95% CI and 80% power, the sample size = 166/group for PFOS

Assuming a 95% CI and 80% power, the sample size = 4,716/group for PFHxS

Sample sizes for the categorical outcomes in Table 2 were based on the following prevalences in adults:

Hypercholesterolemia: 15% Hyperuricemia: 24% Thyroid disease: 6.5% (reported and confirmed by medical records); 11.5% (reported only) Elevated ALT: 11.2% Elevated GGT: 14% Elevated bilirubin: 1.1% Osteoporosis: 5% Osteoarthritis: 7.6% Cardiovascular disease: 13% Ulcerative colitis: 0.5% Rheumatoid arthritis: 1.2%

Health related Endpoints Not shown in Table 2:

Chronic kidney disease: 1.4% Liver disease: 2% Hypertension: 37% Pregnancy-induced hypertension: 8.5% Endometriosis: 7% Lupus: 0.2% Multiple sclerosis: 0.32% Kidney cancer: 0.3%

Multi-site Study – Eligibility Screening Script

Multi-site Study Eligibility Screening Script Flesch-Kincaid Readability Score – 5.8

> Form Approved OMB No. 0923-XXXX Exp. Date xx/xx/201x

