Attachment 8.

Thank you so much. To get you prepared for the appointment, I have just one more question about some medicines [you/your child/both you and your child] might be taking now.

- Are [you/your child/either you or your child] taking any medication for diabetes?
 - YES > Because [you/your child/both you and your child] take diabetes medication, we want to give special instructions about your appointment(s). We will be mailing out a reminder card. If [you/your child/both you and your child] can fast and take your medication without eating, please do. If [you/your child/both you and your child] cannot fast, please eat, and take your medications as usual. Please eat only fat-free or low-fat food, if possible. Please write down the time and the foods you eat. You may drink water during this time. [GO TO CLOSING REMARKS]
 - NO > Please remember not to eat for at least 8 hours before your appointment. You may drink water during this time. We also want to remind you to collect your urine sample(s) that morning and bring it. We will be mailing out a reminder card. [GO TO CLOSING REMARKS]

[CLOSING REMARKS FOR OFFICE VISIT] Don't forget to bring all your medications with you to your appointment. [For children – Don't forget to note the dates of (his/her) vaccinations. We will be asking about that.] Please let us know as soon as possible if you have to cancel your appointment. You can call at [STUDY TELEPHONE NUMBER] if you have to cancel your appointment. Thank you for being part of our study.

[CLOSING REMARKS FOR HOME VISIT] Don't forget to gather all your medications for your appointment. [For children – Don't forget to note the dates of (his/her) vaccinations. We will be asking about that.] Please let us know as soon as possible if you have to cancel your appointment. You can call at [STUDY TELEPHONE NUMBER] if you have to cancel your appointment. Thank you for being part of our study.

Note: This script cannot be used as a voicemail message.

Multi-site Study Appointment tracking form

Adult Study ID No.	Order	Drder		Completed		Clinic or In-field	
 Child Study ID No. 	Assigned by Coordinator	Comments	Date mm/dd/yy	Time hh:mm	0 cl 1 ha	'inic ome	
Informed Consent	1.		_ _ / _ _ / _ _	AM _ _ : _ PM	0	1	
Update Contact Information	2.		_ _ / _ _ / _ _	AM _ _ : _ PM	0	1	
Blood Draw/ Urine Collection	[]		_ _ / _ _ / _ _	AM _ _ : _ PM	0	1	
Assess Current Medication	[]		_ _ / _ _ / _ _	AM _ _ : _ PM	0	1	

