Section F: Child's Medical History

F1. Have you ever been told by a doctor or other health care provider that your child has or had any of the following medical conditions? Fill out the table below. Circle appropriate response and ask the respondent to specify as directed.

м	edical condition		If yes, what year was your child diagnosed?
-		Yes (Please specify)	year
a. Ca	ancer?	No Don't know	
b. All	lergies?	Yes (Please specify) No Don't know	year
c. At	copic dermatitis/eczema?	Yes (Please specify) No Don't know	year
d. As	sthma?	Yes No Don't know	year
e. Ch (rł	nronic stuffy/runny nose hinitis/sinusitis)?	Yes No Don't know	year
f. Hi	gh cholesterol?	Yes No Don't know	year
g. Th	nyroid disease?	Yes (Please specify) No Don't know	year
h. De	elayed puberty?	Yes (Please specify) No Don't know	year
i. Ot	besity?	Yes No Don't know	year
j. Lu	ipus	Yes No Don't know	year
k. Ce	eliac disease	Yes No Don't know	year
l. Cr	ohn's disease	Yes No Don't know	year
m. Di	abetes	Yes, Type 1 Yes, Type 2 Yes, Type unknown No Don't know	year

	Medical condition		If yes, what year was your child diagnosed?
n.	Scleroderma	Yes No Don't know	year
0.	Attention deficit hyperactivity disorder (ADHD) or attention deficit disorder (ADD)?	Yes No → go to p Don't know → go to p	year
p.	How is your child treated for ADHD or ADD?		year
q.	Other learning or behavioral problems?	Yes (Please specify) No \rightarrow go to Question F2. Don't know \rightarrow go to Question F2.	year
r.	How is your child treated for their learning or behavioral problems?		

F2. What age was your child last vaccinated for:

Diphtheria, Tetanus, Pertussis ("DTaP")	age	Don't know	never was vaccinated
"Tdap" booster Tetanus, Diptheria, Pertussis	age	Don't know	never was vaccinated
Measles, Mumps, Rubella ("MMR")	age	Don't know	never was vaccinated
Tetanus shot (for a puncture wound or cut)	age	Don't know	never was vaccinated

FOR GIRLS ONLY

F3. Has your daughter ever used an oral contraceptive ("birth control pill")?

- ____Yes
- ___No \rightarrow go to Question F5
- ____Don't know \rightarrow go to Question F5
- ____Refused to answer \rightarrow go to Question F5

F4. When did your daughter last use an oral contraceptive ("birth control pill")?

___ Month/Year

F5. At what age did your daughter begin menstruation (have her first period)?

___Age

- ____Has not yet begun to menstruate \rightarrow go to Section G
- ____Don't know
- F6. Does your daughter's period occur regularly (every month)?

____Yes

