ATSDR estimates the average public reporting burden for this collection of information as 20 minutes per response, including the time for reviewing instructions, searching existing data/information sources, gathering and maintaining the data/information needed, and completing and reviewing the collection of information. An agency may not conduct or sponsor, and a person is not required to respond to a collection of information unless it displays a currently valid OMB Control Number. Send comments regarding this burden estimate or any other aspect of this collection of information, including suggestions for reducing this burden to CDC/ATSDR Information Collection Review Office, [name]; ATTN: PRA (0923-xxxx)).

Medical Record Abstraction Form - Adult

Study ID: []	Participant Name: []	Date of Birth:///	SSN: xxx-xx-xxxx
--------------	----------------------	-------------------	------------------

The person named above, or his or her legal representative, has authorized you to release his or her medical records to ATSDR/[institution name] for research purposes. Please check If you have a record that a doctor or other health care provider diagnosed or is treating any of the following medical conditions.

Please fill out the table below. Circle appropriate response and specify requested details as directed. Thank you.

Medical Condition	Record Located (Comments)	Year of Diagnosis or Treatment
a. High cholesterol?	Yes No	
b. Other dyslipidemia?	Yes (Please specify diagnosis) No	
c. Heart disease?	Yes No	
d. Hypertension?	Yes No	
e. Pregnancy induced hypertension?	Yes No	
f. Thyroid disease?	Yes (Please specify diagnosis) No	

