Attachment 17a.

Medical Condition	Record Located (Comments)	
g. Liver disease?	Yes (Please specify diagnosis) No	
h. Kidney disease?	Yes (Please specify diagnosis) No	
i. Diabetes?	Yes (Please specify diagnosis) No	
j. Gestational diabetes?	Yes No	
j. Osteoarthritis?	Yes (Please specify diagnosis) No	
k. Osteopenia or Osteoporosis? Yes (Please specify diagnosis) No		
I. Ulcerative colitis?	Yes No	
m. Rheumatoid arthritis?	Yes No	
n. Autoimmune disease? (i.e. Lupus, Multiple sclerosis, Emphysema, Fibromyalgia, Celiac Disease, Crohn's Disease)	Yes (Please specify) No	
o. Endometriosis?	Yes No	
p. Asthma? Yes No		
q. Cancer?	. Cancer? Yes (Please specify) No	
r. Other cancer?	Yes (Please specify) No	

Multi-site Study Medical Record Abstraction Form Child

Form Approved OMB No. 0923-XXXX Exp. Date xx/xx/201x

ATSDR estimates the average public reporting burden for this collection of information as 20 minutes per response, including the time for reviewing instructions, searching existing data/information sources, gathering and maintaining the data/information needed, and completing and reviewing the collection of information. An agency may not conduct or sponsor, and a person is not required to respond to a collection of information unless it displays a currently valid OMB Control Number. Send comments regarding this burden estimate or any other aspect of this collection of information, including suggestions for reducing this burden to CDC/ATSDR Information Collection Review Office, [name]; ATTN: PRA (0923-xxxx).

Medical Record Abstraction Form - Child

Study ID: []	Participant Name: []	Date of Birth://	SSN: xxx-xx-xxxx
--------------	----------------------	------------------	------------------

The person named above, or his or her legal representative, has authorized you to release his or her medical records to ATSDR/[insert institution name] for research purposes. Please check If you have a record that a doctor or other health care provider diagnosed or is treating any of the following medical conditions.

Please fill out the table below. Circle appropriate response and specify requested details as directed. Thank you.

		Year of
Medical Condition	Record Located (Comments)	Diagnosis or
		Treatment
a Allergies?	Yes (Please specify diagnosis)	
	No	
h Atonic dormatitic/oczoma2	Yes	
	No	
c Asthma?	Yes	
C. Astima:	No	
d Rhinitis?	Yes	
u. minus:	No	
	Yes	
e. High cholesterol?	No	

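### The record-abstraction forms (Attachments 17a and 17b) cannot verify year of diagnosis or tell a refuted report from an unlocated record, and the adult form alone cannot confirm coronary artery disease

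*Protocol*

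**What the plan says.** Sections 1.1.3, 1.2, 3.6.5.1 and 3.6.5.2 make record review the means of confirming conditions that participants or parents report. The instruments are Attachment 17a (adult) and Attachment 17b (child), which the provider fills in.

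- **Instruction.** The provider is asked to check whether they "have a record that a doctor or other health care provider diagnosed or is treating" each listed condition.
- **Date.** One column, "Year of Diagnosis or Treatment".
- **Response.** The column "Record Located (Comments") offers Yes or No. Some items add a request to specify the diagnosis.
- **Adult items.** Thyroid, liver and kidney disease, diabetes and other dyslipidemia carry the specify prompt. Heart disease (item c) and pregnancy-induced hypertension (item e) are plain Yes/No. Pre-eclampsia is not listed.

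Section 3.10 states that an analysis of prevalent cases in a cohort design "which takes into consideration the times of diagnosis will also be conducted". Adult hypothesis 2 in Section 2.5.2 reads "Higher prevalence of coronary artery disease and hypertension (including hypertensive disorders" of pregnancy.

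On a related data-capture point, the reminder script (Attachment 8) asks parents to "note the dates of (his/her) vaccinations" and says the study will ask about them. Item F2 of Attachments 15 and 15a then asks "What age was your child last vaccinated for" each vaccine.

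**The concern.** A provider who took over a long-standing case can truthfully enter a recent treatment year. If that year were taken as onset, exposure accrued after disease began would count as preceding it, in a study whose primary exposure is estimated cumulative serum PFAS (Section 3.10). If it is not taken as onset, it still cannot check the self-reported date: when the two disagree, nobody can tell faulty recall from a treatment year.

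A bare No under a record-located heading can mean that the chart was reviewed and the condition is absent, or that this provider holds nothing on it. The first refutes the report. The second leaves it untested. Treating both as refuted loses true cases; treating both as unverified keeps false ones.

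A Yes for heart disease does not show that the disease is coronary. A provider with a pre-eclampsia record has to decide unaided whether it belongs under pregnancy-induced hypertension. No later analysis can recover distinctions that the form did not record.

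**Working it through.** **1. Forms set against the uses made of them**

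| Needed | Source of the need | What the form returns |
|---|---|---|
| Year of diagnosis | Section 3.10 | Year of diagnosis or of treatment, not marked which |
| Report confirmed, refuted or untested | Sections 1.1.3, 1.2, 3.6.5 | Yes, or a No with two meanings |
| Coronary artery disease | Section 2.5.2, adult hypothesis 2 | Heart disease, Yes/No, no specify |
| Hypertensive disorders of pregnancy | Same | Pregnancy-induced hypertension only |

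The first two rows apply to both forms and the last two to the adult form only.

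**2. The plan's own figure for the nearest endpoint**

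Table 2, cardiovascular disease: prevalence 13%, OR 2.01, alpha 0.05 two-sided, power 80%, 250 per stratum.

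- p1 = 0.13; p2 = p1·OR/(1 − p1 + p1·OR) = 0.2613/1.1313 = 0.2310.
- n = [1.96·√(2·p̄·(1 − p̄)) + 0.84·√(p1(1 − p1) + p2(1 − p2))]² / (p2 − p1)², with p̄ = (p1 + p2)/2, gives 227.
- With the Fleiss continuity correction, (n/4)·[1 + √(1 + 4/(n·|p2 − p1|))]², it gives 246, within 3% of the stated 250.

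The figure is reproduced and is not in dispute.

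**3. Illustration of misclassification**

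The error rates below are assumptions; the documents give none. They are taken as non-differential. For sensitivity Se and specificity Sp, the observed prevalence is p* = p·Se + (1 − p)(1 − Sp). Loss of sensitivity stands for true cases whose record is not located. Loss of specificity stands for non-coronary heart disease counted as a case. The n column uses the continuity correction; the power column does not.

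| Se | Sp | p1* | p2* | OR | n per stratum | Power at 250 |
|---|---|---|---|---|---|---|
| 1.0 | 1.00 | 0.130 | 0.231 | 2.01 | 246 | 0.837 |
| 0.9 | 1.00 | 0.117 | 0.208 | 1.98 | 280 | 0.788 |
| 0.8 | 1.00 | 0.104 | 0.185 | 1.95 | 321 | 0.730 |
| 0.7 | 1.00 | 0.091 | 0.162 | 1.93 | 374 | 0.663 |
| 1.0 | 0.98 | 0.147 | 0.246 | 1.89 | 273 | 0.796 |
| 1.0 | 0.95 | 0.174 | 0.269 | 1.76 | 314 | 0.735 |
| 1.0 | 0.90 | 0.217 | 0.308 | 1.61 | 389 | 0.637 |

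Quartiles of 6,000 adults hold 6,000/4 = 1,500 each. At that size power exceeds 99% in every row. Unlocated records barely move the OR, whereas an over-broad case definition pulls it towards 1. For this endpoint the cost is bias rather than lost power.

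**4. Timing**

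No arithmetic is possible. The documents do not say how often a provider would enter a treatment year or how far it would lie from diagnosis.

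**The case against.** The form is not the only source. Section 3.6.5.2 has adults give, for each condition, the date of diagnosis and the provider who made it. Attachment 15 asks parents for the year of diagnosis. Forms go to the provider the participant names, which narrows the case of a disease diagnosed elsewhere. The response column invites comments, the provider letter (Attachment 17) allows a records review at the office, and the Manual of Procedures (Attachment 12) is a placeholder that may yet set abstraction rules. Most other sections speak of cardiovascular disease, and Attachment 16, the adult questionnaire, is not in the text at hand, so its cardiac and pregnancy detail cannot be judged.

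Much of this stands, and it rules out some stronger readings. A reader might infer that confirmed cases and onset dates will be wrong. The documents do not support that, because nothing says the form's year replaces the self-reported date.

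A reader might also size the problem from Attachment 3b: "Thyroid disease: 6.5% (reported and confirmed by medical records); 11.5% (reported only"). Those are planning prevalences, not yields of this form, and an unreturned form or a refused release is not a No. A third response option would not raise the number confirmed either; it would separate refuted reports from untested ones.

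Finally, a reader might extend the vaccine-date mismatch to the validity of the antibody endpoint. The documents do not say how strongly antibody level depends on time since the last dose.

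The mitigations remain partial. The self-reported date is the item to be verified. Comments do not prompt for the distinction that matters, and on-site review is optional with no stated trigger. The pre-eclampsia question in Section G of Attachment 15 does not fill the gap: under Section 3.6.5.1 that long form is for children whose parent is not an adult participant.

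**Conclusion.** The point holds as a defect of data capture that should be corrected. Used as written, Attachments 17a and 17b cannot verify diagnosis year and cannot distinguish a refuted report from one with no record. Attachment 17a alone cannot confirm coronary artery disease and does not list pre-eclampsia. Confirmed status and timing may be misclassified or remain unverified.

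The size is unknown. The illustrated range for cardiovascular disease, an OR of 2.01 falling to between 1.98 and 1.61, rests entirely on assumed non-differential error rates. The conclusion itself rests on the wording of the forms and on Section 3.10 and hypothesis 2 being carried out as stated. It would weaken if the Manual of Procedures or Attachment 16 supplied the missing distinctions.

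**What to change.** Before OMB and IRB clearance:

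1. In 17a and 17b, split the date column into *year of first diagnosis* and *currently treated (Y/N)*.
2. Replace Yes/No with *confirmed*, *record reviewed, not present* and *no record held*. Count only the second as refuted and keep the third as unverified.
3. In 17a, add a specify-diagnosis prompt to item c and a row for pre-eclampsia.
4. Secondary: have item F2 of Attachments 15 and 15a ask for vaccination dates, to match the reminder script.

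The cost is slightly longer forms for providers, with no added visit or test. The forms still carry placeholder OMB numbers and Attachment 5c lists approvals as pending, so the edits are cheap now. After abstraction the missing distinctions could be recovered only by going back to providers.
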